### 6.5 Ill dataset

All subjects who have met the criteria for having an illness episode, based on criteria set in assessment of primary outcome (11.1). This dataset is a subset of the PP dataset and will be used to analyse the duration of illness.

## 7 General statistical considerations

In the statistical analyses, a p-value less than 0.05 will be considered as statistically significant. If not stated otherwise, all tests will be performed as two-sided tests and two-sided 95% confidence intervals will be produced for the treatment differences. No adjustments for the p-values will be made. Missing values will not be imputed in the analyses.

### 7.1 Examination of subgroups

The following subgroups for the primary endpoint will be investigated: antibody status (four-fold rise in neutralizing antibody titer to the study virus: yes/no), cohort, gender and incidence of wild-type virus.

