8.4.1 PRIMARY ANALYSIS

As the primary analysis, the incidence of rhinovirus-associated illness episodes (Yes/No) between the treatment groups will be investigated. The null hypothesis to be rejected is that there is no relationship between the treatment and the incidence of rhinovirus-associated illness episodes. The hypothesis will be tested by using a chi-square test. In case the cell frequencies, such as the expected number of subjects experiencing an illness episode or the expected number of subjects without any episodes in either of the treatment groups, turn out 5 or lower, a Fisher's exact test will be used for the comparison instead, which is seen as a more suitable method with low expected frequencies.

As a sensitivity analysis a logistic regression will be computed for the same dichotomous response (incidence of rhinovirus-associated illness episodes) but in addition to the treatment effect also adjusted with potential confounding factors. Potential confounding factors can be such as antibody status, amount of virus given on day 0, gender or incidence of wild-type virus.

In the primary analysis a p-value ≤ 0.05 is considered as significant.

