## 5 Statistical hypotheses

The purpose of this study is to support the evidence that the probiotic supplementation is more effective than the effect of placebo in reducing the incidence of rhinovirus-associated illness episodes, i.e., the null-hypothesis to be tested is

$H_0$  : There is no relationship between the treatment and the incidence of rhinovirus-associated illness episodes

$H_1$  : There is a relationship between the treatment and the incidence of rhinovirus-associated illness episodes

The effect of probiotic supplementation is considered shown if the two-sided p-value of the primary statistical analysis is less than 0.05.

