### 6.3 Per protocol (PP) dataset

The PP dataset will consist of all subjects having been randomized to a treatment and receiving the virus challenge on Day 0 (ITT), without any major protocol violation. Subjects with acute neutralizing titer of  $>1:4$ , respiratory virus detected prior to virus and antibiotic use before day 14 will be excluded, and only subjects with study product compliance of  $>80\%$  will be included. The subject classification to PP dataset will be done before opening of the randomisation code. PP dataset is used for all efficacy and exploratory analyses as the primary dataset, thus also for the primary evaluation of study hypothesis (see 20.2.).

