## 11 Analysis of efficacy

### 11.1 Primary efficacy variables

The primary efficacy analysis is comparing the incidence of rhinovirus-associated illness episodes (Yes/No) between the treatment groups. A rhinovirus-associated illness episode is detected in case both the following criteria are met:

- 1) Rhinovirus infection: Isolation of the challenge virus on any of the 5 days (study days 1-5) after virus challenge OR a four-fold rise in the neutralizing antibody titer to the study virus (day 28).
- 2) Symptomatic illness: Based on the modified Jackson criteria a total symptom score of at least 6 over the 5 days (sum of study days 1-5) after virus challenge AND either three days of rhinorrhea or the subjective impression that they have had a common cold illness.

The relationship between the treatment and the incidence of rhinovirus-associated illness episodes will be tested by using a chi-square test. In case the cell frequencies, such as the expected number of subjects experiencing an illness episode or the expected number of subjects without any episodes in either of the treatment groups, turn out 5 or lower, a Fisher's exact test will be used for the comparison instead, which is a more suitable method with low expected frequencies.

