## **11.4 Sensitivity analyses**

As a sensitivity analysis, a logistic regression will be computed for the primary efficacy variable. In addition to the treatment effect also potential confounding factors, such as antibody status, cohort, gender or incidence of wild-type virus, are one by one included to the model as fixed effects. Also, the interaction effect (subgroup\*treatment) will be investigated.

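### SAP 7.1 and 11.4 subgroup and adjust the primary endpoint by a four-fold titre rise that is itself part of that endpoint

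*SAP*

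**What the plan says.** The primary endpoint (SAP 11.1) is composite: "A rhinovirus-associated illness episode is detected in case both the following criteria are met". The first criterion is rhinovirus infection, met by isolating the challenge virus on any of days 1–5 "OR a four-fold rise in the neutralizing antibody titer to the study virus (day 28". The second is symptomatic illness by the modified Jackson criteria.

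SAP 7.1 names the subgroups for that endpoint: "antibody status (four-fold rise in neutralizing antibody titer to the study virus: yes/no), cohort, gender and incidence of wild-type virus". This is the only definition of antibody status in either document.

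SAP 11.4 describes a logistic regression of the primary variable in which "potential confounding factors, such as antibody status, cohort, gender or incidence of wild-type virus, are one by one included to the model", and adds a subgroup-by-treatment interaction. Protocol 8.4.1 is looser and leaves the term undefined: "Potential confounding factors can be such as antibody status, amount of virus given on day 0, gender or incidence of wild-type virus".

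The confirmatory test uses none of these factors. SAP 11.1 states: "The relationship between the treatment and the incidence of rhinovirus-associated illness episodes will be tested by using a chi-square test". SAP 5 ties the success claim to that test alone: "The effect of probiotic supplementation is considered shown if the two-sided p-value of the primary statistical analysis is less than 0.05".

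**The concern.** A confounder has to precede treatment or at least be unaffected by it. The four-fold rise is neither. It compares the Day 0 serum with one drawn at about Day 28, some eight weeks after randomisation on Day -28, and it is a direct consequence of infection, which the product is meant to influence (Protocol 2.2.2 makes infection rate a secondary objective). Everyone with a rise is infected by definition. Those without a rise mix uninfected subjects, who cannot be cases, with infected subjects who shed virus but did not seroconvert. If the product changes the infection rate, that mixture differs between arms and randomisation no longer protects the comparison inside either stratum.

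At stake is the reading of one logistic model, its interaction test and one subgroup row. If the product prevents infection, a real effect could look weaker after adjustment and appear confined to subjects without a rise. If the product changed only the antibody response, the adjusted model could suggest an effect on illness that does not exist.

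**Working it through.** **The plan's own figure.** For 60% v 40%, two-sided 0.05 and 80% power, the unpooled formula gives n = (1.960 + 0.842)² × (0.6×0.4 + 0.4×0.6) / 0.2² = 94.2, so 95 per arm as stated in Protocol 8.1 and SAP 4. The pooled formula gives 97, and power at 95 per arm is 79.2%. The antibody factor plays no part in this.

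**Inputs from the documents.** Protocol 8.1: control infection about 90%, and about 67% of the infected ill (0.90 × 0.67 = 0.603). True effect 60% to 40%, so the odds ratio (OR) is (0.4/0.6)/(0.6/0.4) = 0.44. Allocation 1:1 (Protocol 3.3).

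**Assumptions.** The probability s of a four-fold rise given infection is not in the documents and is varied from 0.5 to 0.9. The rise is taken as independent of illness given infection. The mechanism is varied, because the documents do not fix it.

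**Formulas.** With infection rate I and illness given infection q in an arm:
- Rise = yes: P(ill) = q.
- Rise = no: P(ill) = q·I·(1−s)/(1−I·s).
- Adjusted OR: the treatment coefficient from a large-sample logistic fit of illness on treatment and rise.
- Rejection: 3,000 simulated trials at 95 per arm, two-sided 0.05.

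**Worked case: effect wholly through infection (I from 0.9 to 0.6, q = 2/3), s = 0.8.**
- Rise = yes: 0.667 in both arms, OR 1.00.
- Rise = no: placebo 0.667×0.9×0.2/0.28 = 0.429; probiotic 0.667×0.6×0.2/0.52 = 0.154; OR = (0.154/0.846)/(0.429/0.571) = 0.24.
- Adjusted OR 0.61.

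**Across mechanisms.** The true OR is 0.44 except in the null row. Without the rise term the logistic model rejects in 79–81% of trials (4–5% under the null).

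| Mechanism | s | OR, rise | OR, no rise | Adjusted OR | Rejection, adjusted |
|---|---|---|---|---|---|
| Infection only (90% to 60%) | 0.5 | 1.00 | 0.33 | 0.50 | 64% |
| | 0.65 | 1.00 | 0.29 | 0.53 | 54% |
| | 0.8 | 1.00 | 0.24 | 0.61 | 35% |
| | 0.9 | 1.00 | 0.21 | 0.71 | 17% |
| Mixed (infection 90% to 73.5%, fewer ill if infected) | 0.5 | 0.60 | 0.39 | 0.46 | 74% |
| | 0.8 | 0.60 | 0.32 | 0.49 | 63% |
| Symptoms only | 0.5 | 0.40 | 0.48 | 0.44 | 80% |
| | 0.9 | 0.40 | 0.58 | 0.42 | 82% |
| Full null | 0.5–0.9 | 1.00 | 1.00 | 1.00 | 4–5% |

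**Variants.**
- Rise more likely in the ill (75% v 45%, or 90% v 60%, among the infected): adjusted OR 0.58 and 0.72 for the infection mechanism, 0.43 and 0.42 for symptoms only.
- Product lowers the rise rate among the infected from 0.8 to 0.6 and changes nothing else: adjusted OR 1.16 with 7.2% rejection, against 1.00 and 4.6% without the rise term.
- Infection moves as shedding did in the earlier challenge trial (91% to 76%, Protocol 1.1), with q unchanged: true OR 0.67; adjusted OR 0.70–0.76 for s from 0.5 to 0.8.

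**The case against.** The strongest reply is that little depends on this. The success rule rests on the unadjusted chi-square test, and the endpoint is repeated in the ITT set (SAP 20.2). Factors enter one by one, so the cohort and gender models contain no rise term. The rise is neither necessary for the endpoint (virus isolation also counts) nor sufficient (symptoms are required). All of this stands and limits the scope.

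Section 11.4 also does not repeat the definition in 7.1, and Protocol 8.4.1 could mean a pre-challenge titre. But 7.1 is the only definition available, and the interaction term in 11.4 refers back to the subgroups. The inference is reasonable, though not explicit.

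The largest distortions need infection to fall from 90% to 60%, which no document states. The earlier trial saw shedding of 76% v 91% and no effect on antibody responses or symptom severity, so the mechanism is open. This also stands, and it is why the size must be given as a range.

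A reader might also infer that the wild-type-virus factor cannot be estimated in the PP set, since SAP 6.3 says subjects with "respiratory virus detected prior to virus and antibiotic use before day 14 will be excluded" and viral PCR is scheduled only on Day 0. The documents do not support that firmly. They never say how wild-type virus is determined, and rhinovirus culture continues on days 1–5. At most the factor needs a definition.

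**Conclusion.** The point holds for one factor. Following the SAP conditions the primary endpoint on a post-randomisation component of itself, and calling that component a confounder is a mistake. The antibody-status subgroup, the model containing it and its interaction have no clear interpretation.

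The possible bias runs from none (full null) through slight (symptoms only) to severe (infection only, high seroconversion). These sizes rest on the planning rates in Protocol 8.1, an assumed 50–90% seroconversion rate and an assumed mechanism.

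It would be tempting to conclude that the sensitivity and subgroup results as a whole will be wrong, or that 11.4 would contradict a true positive finding. Neither follows. The other models are separate, and in every scenario with a true benefit the adjusted odds ratio stays below 1. Even in the infection-only case part of the effect survives, because infections shown by virus isolation without a rise remain in the no-rise stratum. The loss is of size and power, not direction.

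**What to change.** In SAP 7.1 and 11.4, remove the four-fold rise as subgroup, covariate and interaction factor for the primary endpoint. Then do one of two things:

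- Drop antibody status. Protocol 8.4.1 offers it only as an example of a possible factor.
- Define it as the screening neutralising titre, the only one taken before randomisation. State that its range is narrow because entry requires 1:4 or less, so it may carry little information. The Day 0 titre is not an equivalent substitute, since it follows 28 days of product.

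Add a sentence that the primary endpoint is adjusted only for variables fixed before randomisation. Results by four-fold rise may be tabulated descriptively, without a treatment test.

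The cost is a few sentences in the SAP, entered before the treatment code is opened and recorded in SAP 15. No new data are needed, since screening serology already exists. The primary test and the 95 per arm do not change.

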4.2.2 Study periods

Screening:

- Consent and enrollment (approximately 375 subjects)
- Medical history questionnaire and demographics
- Vital signs and brief physical exam
- Physical activity question
- Review of inclusion/exclusion criteria
- Blood draw for screening neutralization antibody titer (if no antibody screening test has been done in the last 12 weeks)

Day -42 ± 4:

- All subjects begin dietary “run-in” period

Day -28 ± 4: Seronegative subjects only

- Review of inclusion/exclusion criteria
- Pre-probiotic baseline nasal lavage for IL-8 and other cytokines
- Pre-probiotic baseline nasal swab for microbiomics
- Pre-probiotic baseline throat swab for microbiomics
- Blood draw for pre-probiotic transcriptomics studies
- Assessment of concomitant medications
- Randomized to active or placebo probiotic
- Urine pregnancy screen for females

Day -21 ± 2

- All subjects return to study site for new supply of probiotic and compliance review
- AE assessment
- Assessment of concomitant medications

Day -14 ± 2:

- All subjects return to study site for new supply of probiotic and compliance review
- Nasal lavage for multiplex cytokine assays
- AE assessment
- Assessment of concomitant medications

Day -7 ± 2:

- All subjects return to study site for new supply of probiotic and compliance review
- AE assessment
- Assessment of concomitant medications

Day 0:

- Review of inclusion/exclusion criteria
- Assessment of blinding
- AE assessment
- Assessment of concomitant medications
- Urine pregnancy screen for females
- Stool specimen for probiotic compliance and microbiomics
- Nasal swab for microbiomics
- Throat swab for microbiomics
- Throat swab for culture
- Nasal lavage for unanticipated viruses
- Nasal lavage for pre-RV challenge baseline IL-8
- Blood draw for measurement of neutralizing antibody
- Blood draw for pre-RV challenge transcriptomics
- Nasal lavage for multiplex cytokine assays
- Symptom assessment
- Challenge with rhinovirus
- Compliance check/resupply
- Continue probiotic treatment

Day 1-4:

- AE assessment
- Assessment of concomitant medications
- Nasal lavage for quantitative rhinovirus culture
- Nasal lavage for IL-8 measurement
- Nasal lavage for multiplex cytokine assays
- Symptom assessment
- Assessment of the effect of symptoms on physical activity
- Nasal swab for microbiomics (day 3)
- Throat swab for microbiomics (day 3)
- Blood draw for post-RV challenge transcriptomics (Day 2 only)
- Continue probiotic treatment

Day 5:

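### SAP 7.1 and 11.4 use post-challenge seroconversion, itself a component of the primary endpoint, as subgroup factor, covariate and interaction term

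*SAP*

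**What the plan says.** SAP 7.1 opens its list with "The following subgroups for the primary endpoint will be investigated", and the first factor is "antibody status (four-fold rise in neutralizing antibody titer to the study virus: yes/no". This is the only definition of antibody status in either document.

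SAP 11.1 requires both infection and symptomatic illness for the primary endpoint. Infection is isolation of the challenge virus on Days 1–5, "OR a four-fold rise in the neutralizing antibody titer to the study virus (day 28").

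SAP 11.4 plans a logistic regression for the primary variable in which "potential confounding factors, such as antibody status, cohort, gender or incidence of wild-type virus, are one by one included to the model". It continues: "Also, the interaction effect", written there as subgroup by treatment, which ties 11.4 back to the list in 7.1.

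Protocol 8.4.1 has the same idea without a definition: "Potential confounding factors can be such as antibody status, amount of virus given on day 0, gender or incidence of wild-type virus".

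The Day 0 visit in Protocol 4.2.2 includes "Blood draw for measurement of neutralizing antibody", listed ahead of the virus challenge. The next antibody draw is at the final visit, Day 21 or later.

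**The concern.** A four-fold rise is a response to the challenge virus. It occurs after randomisation, is measured after the Day 1–5 symptom window, and by itself satisfies the infection half of the primary endpoint. A confounder would have to precede treatment or be independent of it; this variable may be changed by treatment.

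Every subject in the rise stratum is infected by definition, so prevention of infection cannot show there. If the product does prevent infection, it moves subjects from the rise stratum to the no-rise stratum. Within strata, the groups are then no longer those that randomisation formed.

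At stake is how the sensitivity section is read. An adjusted OR near 1 could be taken as a sign that the primary result is fragile, and a significant interaction as effect modification, when both come from conditioning on part of the outcome.

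**Working it through.** **Inputs from the documents.** Control infection about 90%, illness among infected controls about 67%, illness 60% versus 40%, 95 completed per arm (Protocol 8.1); two-sided 0.05 (SAP 5); 254 challenged in total (SAP 4), so 127 per arm at 1:1.

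**Assumptions, not in the documents.** The share *s* of infected subjects with a four-fold rise, taken as 60–95%, and the infection rate in the probiotic arm.

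**The plan's own figure.** Unpooled formula: n = (1.96 + 0.84)² × (0.6×0.4 + 0.4×0.6) / 0.2² = 7.849 × 0.48 / 0.04 = 94.2, so 95 per arm. Power at 95 is about 79%. Unadjusted OR = (0.4/0.6)/(0.6/0.4) = 0.44. The stated sample size reproduces.

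**Stratum rates.** With infection rate *i* and illness among the infected *q*, the rise stratum has illness rate *q* and the no-rise stratum has i(1−s)q / (1−is).

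**One case by hand.** Let infection fall from 90% to 60%, q = 2/3 in both arms, s = 0.8.

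- Rise: 66.7% versus 66.7%. Expected ill/not ill: placebo 45.6/22.8, probiotic 30.4/15.2. Log OR 0, variance 0.164.
- No rise: placebo 0.12/0.28 = 42.9%; probiotic 0.08/0.52 = 15.4%. Expected ill/not ill: 11.4/15.2 and 7.6/41.8. Log OR = ln(0.182/0.75) = −1.417, variance 0.309.
- Adjusted effect, inverse-variance weights 6.08 and 3.24: −1.417 × 3.24/9.32 = −0.49, OR 0.61; SE 0.328, z = 1.50, power about 32%.
- Interaction: 1.417/√(0.309 + 0.164) = 2.06, power about 54%.

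**Simulation, 95 per arm, 4,000 trials per setting.** Logistic model with treatment and seroconversion; likelihood-ratio test for the interaction. Entries are for s = 60/80/90/95%. Repeat runs move the percentages by a point or two.

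| Mechanism | Adjusted OR | Power of adjusted test, % | Interaction significant, % |
|---|---|---|---|
| Infection 90% to 60% (assumed) | 0.52/0.61/0.71/0.82 | 56/34/18/10 | 46/55/48/38 |
| Mixed: infection 90% to 75% (assumed) | 0.46/0.48/0.51/0.53 | 74/66/58/50 | 11/13/13/14 |
| Only illness among the infected falls | 0.44/0.43/0.42/0.42 | 79/80/81/82 | 7/8/8/9 |
| No effect | 1.00 throughout | 5–6 (false positives) | 5–7 |

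At 127 per arm, with infection 90% to 60% and s = 0.8, power falls from about 89% unadjusted to 44% adjusted, and the interaction is significant in about 69% of trials.

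**With a pre-challenge covariate instead** (assumed 50% prevalence, OR with illness 1 to 0.33): adjusted OR 0.44–0.42, power 79–82%, interaction significant in about 5%.

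**The case against.** The strongest reply has four parts.

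- **The primary inference is untouched.** It rests on an unadjusted chi-square test. No decision rule attaches to the subgroup table or the sensitivity model, and because factors "are one by one included to the model as fixed effects", the cohort, gender and wild-type models do not inherit the problem. This stands, and it limits the severity.
- **The distortion is conditional.** A reader might infer that a real effect will be adjusted away and a false interaction will appear. The documents do not support that. They give an infection rate for the control arm only; the fall to 60% is an assumption. The earlier challenge study (Protocol 1.1) points both ways: shedding was 76% versus 91%, but there was no effect on serum antibody responses. If the product only reduces illness among the infected, almost nothing changes.
- **There is no earlier definition.** A reader might infer that the SAP redefined a protocol term and failed to declare it in section 15. Protocol 8.4.1 never defined antibody status. Its neighbours in that sentence do not settle the meaning either, since the timing of wild-type virus is not stated.
- **A baseline replacement may have little to work with.** Eligibility requires a titre of 1:4 or less, and the per-protocol (PP) set excludes acute titres above 1:4 (SAP 6.3). A split at 1:4 is therefore constant in the primary dataset, and the documents do not say whether the assay grades below it. The fix needs a fallback.

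None of this makes a post-challenge endpoint component a confounder. The mechanism cannot be known in advance, so the model would be hard to interpret whichever way it came out.

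**Conclusion.** The point holds as a should-fix. That the variable arises after challenge, forms part of the endpoint and is used in three roles (subgroup, covariate, interaction) follows from SAP 7.1, 11.1 and 11.4 without any assumption.

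The numerical damage rests on two assumptions: the seroconversion share and how far the product lowers infection. It is severe if the whole effect comes through infection, moderate if the mechanism is mixed, and essentially nil if the product acts only on illness among the infected or has no effect. The scenario is a live one, because infection rate is a secondary objective of this trial. The primary test, its type I error and the sample size are unaffected.

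**What to change.** 1. In SAP 7.1 and 11.4, delete the four-fold rise as subgroup, covariate and interaction factor.
2. Define antibody status from the pre-challenge Day 0 titre, using a grading finer than 1:4 if the assay provides one. A split at 1:4 is usable only in the ITT set, where the number above the cut-off is not given and may be small.
3. If no usable grading exists, drop the factor.
4. Label any results by seroconversion as descriptive only. Antibody response stays an outcome through the titre-change analysis in SAP 11.3.

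The cost is SAP wording before the code is opened, plus a check with the laboratory on how titres at or below 1:4 are recorded. The Day 0 sample is already planned, so no new data collection is needed.
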